volunteers will be blinded to the conditions. During each session, volunteers will first perform a task training and a short (approx. 5 min) block of the approach/avoidance task (Ap/Av) without TMS to record intrinsic EEG activity and use it for calibrating the real-time TMS-EEG system (Shrinpour et al., 2020). Then, volunteers will perform 8 main blocks of approach/avoidance tasks with TMS (approx. 6 minutes per block) in randomized order: 1. congruent task + TMS at theta peaks, 2. congruent task + TMS at theta troughs, 3. incongruent task + TMS at theta peaks, and 4. incongruent task + TMS at theta troughs. During each task trial, the volunteer will receive a single burst of TMS (up to three pulses) at the peak or trough of ongoing theta rhythm. In the verum TMS-EEG condition/block, we will apply TMS pulses over the left DLPFC based on the left DLPFC theta oscillations. In the sham condition/block, TMS will be applied over the head vertex (which should not induce changes in the prefrontal activity but will induce the same sensory effects). EEG will be recorded throughout the TMS-EEG sessions. In addition, electrooculography and heart rate will be recorded together with EEG using non-invasive sensors for the accurate removal of ocular and cardiac artifacts. There will be 3-5 min breaks in-between the blocks for rest. The total number of TMS pulses per day will not exceed 3,000 pulses, many times lower than the established safety limit of 90,000 pulses per day (Cole et al., 2022, 2020).

[figure not shown]

Diagram 1: Experimental pipeline with timing.

5.2. Study Procedures:

5.2.1. Initial questionnaires: during the initial visit, each volunteer will fill out standardized self-reported questionnaires regarding their demographic data and emotional assessment. These include the Patient Health Questionnaire (PHQ-9), General Anxiety Disorder (GAD-7) tool, and Quick Inventory of Depressive Symptomatology – Self-Rated (QIDS-SR-16). Total time necessary to complete all questionnaires is approx. 25 minutes.

5.2.2. MRI: During the first session, 3T MRI scans will be performed at the Center for Magnetic Resonance Research (CMRR). Participants will

MEDICAL PROTOCOL (HRP-590)

PROTOCOL TITLE: Investigating the causal and phase-dependent role of prefrontal theta oscillations in approach/avoidance behavior

VERSION DATE: 14/09/2024

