- 5.2.4. TMS – motor threshold: To individualize the stimulation intensity before every TMS-EEG session, we will apply single-pulse stimulation to the motor hotspot for the FDI muscle in the left motor cortex (M1). The volunteer will be asked to relax his right hand. The lowest intensity at which 3 out of 6 pulses result in the motor evoked potential will be considered a resting motor threshold. This step will take approx. 15 minutes to perform.
- 5.2.5. TMS – experiment: During the Ap/Av test, we will apply single bursts of TMS (up to three pulses) every task trial at either peak or trough of prefrontal theta oscillation. The theta signal will be recorded in the frequency band from 3 to 7 Hz from the AF3/F3 electrodes (according to the international 10-10 convention) using a Laplacian electrode-montage. The stimulation will be applied with the intensity of up to 120% of the resting motor threshold (which is a safe and common practice; Rossi et al., 2021). The intensity can be decreased for individual participants. In the verum TMS-EEG condition, we will apply TMS pulses over the left DLPFC based on the left DLPFC theta oscillations (Figure 2). In the sham condition, TMS will be applied over the head vertex (which should not induce changes in the prefrontal activity but will induce the same sensory effects). In total, 8 task/stimulation blocks will be performed per session, each approx. 6 minutes long with 1 burst of TMS every 2-6 seconds (= every task trial). Stimulation will be performed by the investigators listed in the present protocol after safety and application training by the principal investigator and under his oversight. TMS stimulation will follow the guidelines of the International Federation of Clinical Neurophysiology (Rossi et al., 2021).

MEDICAL PROTOCOL (HRP-590)

PROTOCOL TITLE: Investigating the causal and phase-dependent role of prefrontal theta oscillations in approach/avoidance behavior

VERSION DATE: 14/09/2024

5.2.6. Physiological recordings: EEG will be recorded throughout the whole experimental session at a high sampling rate ($\geq 1,000$ Hz) using a 24-bit amplifier with active electrodes and electrode caps of appropriate size. No hardware filtering will be used.

Electrooculography and heart rhythm will be recorded together with EEG using non-invasive sensors synchronized with the EEG acquisition.

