MEDICAL PROTOCOL (HRP-590)

PROTOCOL TITLE: Investigating the causal and phase-dependent role of prefrontal theta oscillations in approach/avoidance behavior

VERSION DATE: 14/09/2024

appropriate guidelines are followed. To protect participants from possible risks, we will do as follows:

Head and neck aches: Minimize TMS intensity and avoid sensitive areas of scalp muscles and nerves to avoid head and neck aches.

Transient hearing changes: Earplugs will be offered to subjects and investigators during TMS to prevent transient hearing shifts caused by TMS.

Seizures: Screening and enrollment procedures will exclude subjects for whom TMS is contraindicated, those who are at increased risk of seizure, or those for whom the potential consequences of a seizure are increased. The informed consent process will note the potential risk of seizures.

There is no evidence that a TMS-induced seizure increases the risk of having a second seizure in an otherwise healthy individual. In all lab spaces, we have a plan of action in place in the case of a seizure (based on NIH recommendations) as follows:

1. Roll the person on their side to prevent them from choking on fluids or vomit.
2. Cushion the individual's head.
3. Loosen any tight clothing around the neck.
4. Do not restrict the person from moving or wandering unless they are in danger.
5. Do not put anything in the person's mouth – it can cause choking and trauma.
6. Remove any dangerous objects the person might hit or walk into during the seizure.
7. Call 911.
8. Note how long the seizure lasts and what symptoms occurred then report this information to emergency personnel.
9. Stay with the person until the seizure ends and emergency personnel arrive and take over.

13.2. Reproduction Risks: No reproduction risks of TMS have been previously reported or suggested in the literature.

13.3. Risks to Others: No risks to others during or after TMS have been previously reported or suggested in the literature.

14. Potential Benefits to Participants

MEDICAL PROTOCOL (HRP-590)

PROTOCOL TITLE: Investigating the causal and phase-dependent role of prefrontal theta oscillations in approach/avoidance behavior

VERSION DATE: 14/09/2024

- 14.1. Potential Benefits: There are no direct benefits for the participant in this study.

15. Statistical Considerations

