- 18.3. Unblinding procedures: This study follows a crossover design, with verum and sham conditions administered in intermittent blocks in randomized order. Thus, each participant will experience all study procedures. The exact sequence of procedures is stored in a computer file. In an unlikely case of adverse events, the study's principal investigator will access the specific file and reveal the sequence of procedures preceding the event to the response team and overseeing bodies.

19. Provisions to Protect the Privacy Interests of Participants

- 19.1. Protecting Privacy: We will obtain personal information about the volunteer necessary for the study (day of enrollment, name, age and date of birth, biological sex at birth, handedness, phone number, email, screening results regarding study criteria) and store it in paper form and in an encrypted electronic form in the Department of Biomedical Engineering separately from other data. This information will not be shared with any 3rd party, and the volunteers' enrollment in the study will not be disclosed to anyone outside the investigation group. The investigators in the study will contact volunteers through the course of the study to arrange the experimental session via the volunteers' phone or email. The volunteers will be informed prior to their participation that the application of physiological recordings and transcranial magnetic stimulation will require an investigator to touch their head, face, arms, and hands while setting up the equipment.

- 19.2. Access to Participants: We will not collect PHI about the volunteers from their medical records or any other sources outside this study. The information that is necessary for the study will be obtained by the investigators directly from the participants during the initial meeting and the experimental sessions.

20. Compensation for Research-Related Injury

MEDICAL PROTOCOL (HRP-590)

PROTOCOL TITLE: Investigating the causal and phase-dependent role of prefrontal theta oscillations in approach/avoidance behavior

VERSION DATE: 14/09/2024

20.1. Compensation for Research-Related Injury: No specific compensation scheme for research-related injury is planned.

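### Participants can be blind to theta phase but not to the scalp site stimulated, so the real-versus-control main effect lacks the blinding that sections 5.1 and 5.2.5 imply

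*Combined protocol and SAP*

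**What the plan says.** Section 5.1 sets verum and sham blocks in random order and states that "volunteers will be blinded to the conditions". The two conditions are defined by location. For verum: "In the verum TMS-EEG condition/block, we will apply TMS pulses over the left DLPFC based on the left DLPFC theta oscillations". For sham: "In the sham condition/block, TMS will be applied over the head vertex". The only support for equivalence is the remark, made in both 5.1 and 5.2.5, that vertex stimulation "which should not induce changes in the prefrontal activity but will induce the same sensory effects". No reference or procedure accompanies it.

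Section 18.3 confirms the within-participant layout, "with verum and sham conditions administered in intermittent blocks in randomized order", and adds that "each participant will experience all study procedures". Sections 5.1 and 5.2.5 give 8 blocks of about 6 minutes, and 5.2.5 gives one burst every 2 to 6 seconds.

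Section 15.3 enters real versus control and peak versus trough as categorical factors in the GLMM for the HDDM parameters, followed by pairwise tests between conditions. It names no interaction between the two factors.

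**The concern.** Blinding to a condition requires that the participant cannot tell the conditions apart, or at least cannot tell which is which. Here they differ by the place on the head where real pulses are felt, and each participant receives both in one sitting. Someone stimulated on the left frontal scalp in some blocks and on the top of the head in others can be expected to notice the change.

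The primary outcome is reaction time (3.1, 5.2.3), which discomfort, distraction or expectation can shift. If these differ by site, the real-versus-control main effect mixes them with any effect of stimulating prefrontal cortex. What is at stake is how that main effect is interpreted: described as sham-controlled and participant-blinded, it would appear to exclude explanations that the design does not exclude.

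**Working it through.** The plan gives no figure for blinding or sensory equivalence, so there is none to reproduce. The check sets the text side by side and then asks which contrasts an unmasked site difference can reach.

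**Step 1: what the text provides for masking**

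| Element | Where | What is described |
|---|---|---|
| Stimulation | 4.1, 5.1, 5.2.5 | Figure-8 coil; real pulses at both sites; no placebo coil or concealment of position |
| Sensory equivalence | 5.1, 5.2.5 | Asserted; no matching or rating |
| Sound | 13.1.2 | Earplugs offered; these do not mask scalp location |
| Scalp sensation | 13.1.2 | Plan to "avoid sensitive areas of scalp muscles and nerves to avoid head and neck aches", which accepts that sensation depends on location |
| Post-session questionnaire | 5.2.7 | Adverse effects; no item on perceived condition |

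Nothing here stops a participant from noticing the site. Phase is different: it is set in real time from the EEG, with the site unchanged between peak and trough, so blinding to phase is plausible.

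**Step 2: which contrasts are exposed**

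Let the mean reaction time at site s (D = DLPFC, V = vertex), phase p and task t be m(s,p,t) + b(s), where b(s) is a sensory or expectation shift that depends on site only.

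- Real versus control, averaged over phase and task: true difference + [b(D) − b(V)]. The whole shift enters.
- Peak minus trough within a site: b(s) − b(s) = 0.
- Site-by-phase interaction: [b(D) − b(D)] − [b(V) − b(V)] = 0.
- Congruent minus incongruent within a site: b(s) − b(s) = 0.

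As an assumed example, b(D) − b(V) = 10 to 20 ms biases the site main effect on overall reaction time by 10 to 20 ms and the other three contrasts by 0. The last two zeros are conditional. The interaction is protected only if the shift is the same at peak and trough, and the congruency difference only if it is the same in both tasks. Milliseconds do not carry over directly to drift rate or decision threshold, which are what 15.3 compares.

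**Step 3: illustration in standardised units**

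Assume no neural effect, a two-sided 5% paired test, and n = 26 (15.2). Let δ be the shift divided by the SD of the paired real-minus-control difference. Reject when |T| > 2.06 (25 df), with T noncentral t and noncentrality δ√26.

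| δ (assumed) | δ√26 | Probability of rejecting |
|---|---|---|
| 0 | 0 | 5% |
| 0.1 | 0.51 | 8% |
| 0.2 | 1.02 | 17% |
| 0.3 | 1.53 | 31% |
| 0.5 | 2.55 | 69% |

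The documents give no value for δ. The table shows sensitivity and does not estimate the bias.

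**Step 4: precision of the interaction**

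Assume the four site-by-phase means have independent errors with equal variance v. Peak minus trough within DLPFC then has variance v + v = 2v, and the interaction has 4v. The SD ratio is √(4v/2v) = √2 = 1.41. If the within-DLPFC contrast has d = 0.5 and vertex shows no phase effect, the interaction has d = 0.5/1.41 = 0.35. By the formula in step 3 (0.354 × √26 = 1.80), power at n = 26 is 41%, against 69% at d = 0.5.

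**The case against.** The strongest reply is that the purpose (1.1) and the primary endpoint (3.1) concern peak versus trough, where blinding is plausible, and that the plan nowhere makes the real-versus-control main effect the basis of its causal claim. This stands and limits the point to the control contrast.

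A second reply is that noticing the site is not the same as knowing the condition. Both sites receive real TMS, and blinding could mean not knowing which site is the active one. This also stands in part. A reader might infer that participants know which condition is verum because procedures are explained beforehand. Sections 8.3 and 21.1 say only that procedures are explained and understood, and the consent pages are not available. However, masking of that kind is weaker than what 5.1 states, and the plan does not describe it.

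Three other inferences go further than the text:

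- Section 13.1.2 does not compare DLPFC with vertex. It is a safety measure stating an intention to avoid sensitive areas, and 5.1 and 5.2.5 allow intensity to be lowered for individuals. It shows only that location matters to sensation.
- The text does not say whether one coil is moved or two are used. The scalp site changes either way.
- Facial twitching from TMS is not mentioned and is not relied on here.

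Finally, any bias figure is assumed, and equal slowing in both tasks leaves the congruency difference, itself a primary test outcome in 5.2.3, untouched. Both remarks are correct.

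**Conclusion.** The concern holds in a limited form. The plan states blinding to the conditions, but what it describes secures at most blinding to theta phase and possibly to which site is active. It does not secure blinding to the site stimulated. The real-versus-control main effect in 15.3, on overall reaction time and the HDDM parameters derived from it, can therefore include sensory or expectation differences. Their size and direction cannot be obtained from the documents.

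This rests on one assumption beyond the text: that a participant can feel the difference between left frontal and vertex stimulation. A reader might conclude that the trial's central phase question is compromised. The documents do not support that, because peak versus trough within a site involves no change of site.

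The matter is worth correcting because 15.3 uses real versus control as a factor and does not name the interaction that would separate a site-specific phase effect from a general site difference.

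**What to change.** 1. In 5.1 and 5.2.5, state that participants are blind to theta phase and not to stimulation site. Call vertex an active control site. Either support the claim of equal sensory effects or remove it. If participants are also kept unaware of which site is the active one, say so and say how.
2. In 15.3, add the site-by-phase interaction to the GLMM. Rest the conclusion about a prefrontal phase-specific effect on that interaction together with peak versus trough within DLPFC. Treat the real-versus-control main effect as descriptive.
3. Optionally, add a short item on perceived condition and sensation. Per block is better than end of session, because one closing question cannot separate 8 alternating blocks.

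The cost is wording, one model term and, if adopted, a brief questionnaire item; stimulation does not change. The blinding statement becomes less favourable. The interaction is also less precise than the within-DLPFC phase contrast, by the factor of about 1.41 in SD shown above under its assumptions, so section 15.2 should say which contrast the sample size of 26 is meant to serve.

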- 2.2. Preliminary Data: We have developed a real-time TMS-EEG system which can continuously monitor the prefrontal theta rhythm (3-7 Hz) and trigger TMS pulses at specific phases with high accuracy. Our system has been validated in computational simulations and in proof-of-concept study in

MEDICAL PROTOCOL (HRP-590)

PROTOCOL TITLE: Investigating the causal and phase-dependent role of prefrontal theta oscillations in approach/avoidance behavior

VERSION DATE: 14/09/2024

healthy adults (Shirinpour et al., 2020). Recently, our real-time TMS-EEG system was used to investigate the phase-specific role of ongoing oscillations in motor cortex in adult participants, demonstrating robust performance and no unexpected side effects (Wischnewski et al., 2022).

- 2.3. Existing Literature: The combined application of TMS and EEG has established itself as a potent tool to probe and measure the causality of brain activity. It allows to accurately capture brain responses to the perturbation at specific times relative to the ongoing brain processes or cognitive tasks (Rogasch et al., 2016; Rogasch and Fitzgerald, 2013; Zrenner et al., 2016). Further, several recent studies have investigated the brain neurophysiology using real-time TMS-EEG for probing neural oscillations at different phases (Shirinpour et al., 2020; Schaworonkow et al., 2018; Zrenner et al., 2017). Our lab developed a novel closed-loop algorithm with higher accuracy compared to previous methods (Shirinpour et al., 2020). We recently applied the novel system to test the role of ongoing beta and mu oscillations in the motor cortex in healthy adults (Wischnewski et al., 2022). Moreover, the initial efforts to utilize real-time TMS-EEG for probing prefrontal activity and link between the prefrontal theta and cognition showed effectiveness and safety of such approach (Gordon et al., 2022).

3. Study Endpoints/Events/Outcomes

- 3.1. Primary Endpoint/Event/Outcome: The approach/avoidance test measures (reaction times to positive and negative emotional stimuli) during concurrent probing of ongoing prefrontal theta oscillations at peaks vs. troughs using TMS.
- 3.2. Secondary Endpoint(s)/Event(s)/Outcome(s): TMS-evoked potentials (TEPs) in concurrent EEG during the approach/avoidance test.

4. Study Intervention(s)/Investigational Agent(s)

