lay in the supine position within the scanner and be asked to relax. T1 and T2-weighted images will be collected to provide anatomical models for neural navigation during TMS. In addition, diffusion tensor imaging will be collected to assess structural connectivity of the prefrontal cortex, and BOLD fMRI contrast will be collected during the resting state to assess functional connectivity. All imaging modalities will follow standard Human Connectome Project (HCP) protocols (Harms et al., 2018), as routinely used in CMRR. Overall scanning time will be under one hour.

- 5.2.3. The approach/avoidance (Ap/Av) test: In the Ap/Av task, during each task trial, the volunteer sees on the screen a human face with either positive emotion (happiness, joy), negative emotion (anger, fear), or neutral emotion (Figure 1). During the congruent condition, the volunteer has to pull a joystick towards themself when they see a face with positive emotions and push away when they see negative emotions. In the incongruent condition, the responses with a joystick are the opposite. Neutral emotional stimuli require no response. When a joystick is pulled, the image become larger on the screen (imitating approach), when a joystick is pushed away – it become smaller (imitating avoidance). The reaction times to the stimuli and reaction time difference between the congruent and incongruent conditions constitute the primary test outcomes. We will perform four task blocks (approx. ten minutes each): two with congruent conditions and two with incongruent. The emotional stimuli are taken from publicly available, scientifically validated databases of emotional facial expressions, including Karolinska Directed Emotional Faces (KDEF; Lundqvist et al., 1998) and AffectNet (Mollahosseini et al., 2017). All stimuli can legally be used and redistributed for research purposes. The task presentation PC will be synchronized with the EEG amplifier and TMS machine using TCP/IP, UDP, and/or TTL protocols. Total time per session is 4 blocks of approx. 10 minutes, with approx. 5 minutes breaks in between.

MEDICAL PROTOCOL (HRP-590)

PROTOCOL TITLE: Investigating the causal and phase-dependent role of prefrontal theta oscillations in approach/avoidance behavior

VERSION DATE: 14/09/2024

[figure not shown]

Figure 1. Overview of a single experimental TMS-EEG session.

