Individual or group that is disadvantaged in the distribution of social goods and services such as income, housing, or healthcare.	included but not the focus
Individual or group with a serious health condition for which there are no satisfactory standard treatments.	Excluded
Individual or group with a fear of negative consequences for not participating in the research (e.g.	Excluded

MEDICAL PROTOCOL (HRP-590)

PROTOCOL TITLE: Investigating the causal and phase-dependent role of prefrontal theta oscillations in approach/avoidance behavior

VERSION DATE: 14/09/2024

institutionalization, deportation, disclosure of stigmatizing behavior).	
Any other circumstance/dynamic that could increase vulnerability to coercion or exploitation that might influence consent to research or decision to continue in research.	Excluded

- 9.2. Additional safeguards, if any, to ensure inclusion is appropriate: Students and others who directly work in the Principal Investigator's lab will be excluded from participation.
- 9.3. If research holds prospect for direct benefit to participants, provide justification for any exclusions indicated in the table above: N/A

10. Local Number of Participants

- 10.1. Local Number of Participants to be Consented: We estimate that a sample size of 26 volunteers will allow us to reach the primary endpoints of this study, corresponding to medium effect size, based on previous research (Shirinpour et al., 2020; Gordon et al., 2022).

11. Local Recruitment Methods

- 11.1. Recruitment Process: Recruitment poster will be posted publicly throughout the Twin Cities campus of the University of Minnesota.
- 11.2. Identification of Potential Participants: The potential participant will contact the investigators in this study via the institutional email provided in the recruitment poster.
- 11.3. Recruitment Materials: An advertisement will be posted on advertisement boards in numerous buildings on the Twin Cities campus. The flyer will include a brief description of the study, experimental procedures, monetary compensation, summary of inclusion/exclusion criteria, and an institutional contact email.

MEDICAL PROTOCOL (HRP-590)

PROTOCOL TITLE: Investigating the causal and phase-dependent role of prefrontal theta oscillations in approach/avoidance behavior

VERSION DATE: 14/09/2024

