- 15.1. Data Analysis Plan: We will analyze reaction times from the Ap/Av test using Hierarchical Bayesian Drift Diffusion Models (HDDM). This model is optimal for two alternative forced-choice cognitive tasks. It estimates single-trial performance in the presence of various sources of noise and trial-by-trial variations. The model will take reaction times as inputs and recover the variables of interest – speed of evidence accumulation (drift rate) and the decision thresholds for responding to the stimuli of positive and negative valence.

EEG from the stimulation and task periods will first be preprocessed. We will exclude noisy trials and interpolate noise channels, bandpass filter the signals (0.2-80 Hz) using Butterworth noncausal filters, suppress the line noise, and clean the data with extended InfoMax ICA. After preprocessing and artifact suppression, we will epoch the data around the TMS pulses, and calculate the TMS-evoked potentials in the left DLPFC caused by the stimulation at the peak and trough of theta oscillations.

- 15.2. Power Analysis: We estimated that medium effect size of Cohen's $d = 0.5$, which was observed in comparable studies (Shirinpour et al., 2020; Gordon et al., 2022), will be reached with a sample size of 26 volunteers.

- 15.3. Statistical Analysis: The HDDM parameters will be compared between the conditions using Generalized Linear Mixed-Effect Models (GLMM) with model outcomes as dependent variables, stimulation conditions (real vs control and peaks vs trough) as categorical independent variables, and participant IDs as a nuance variable. Further, post-hoc pairwise nonparametric tests will be applied between the conditions. Latency and magnitude of TMS-evoked potentials (TEPs) will be compared between the conditions using nonparametric cluster-based permutation test with false discovery rate correction for number of comparisons. Outcomes of TEPs and behavioral analysis will be correlated using Spearman statistics.

- 15.4. Data Integrity: Raw data and corresponding log files will be examined by the principal investigator on a regular basis during the data collection stage. The automatic log files will be generated automatically by the software which runs the EEG amplifier. The log files will be cross-checked

MEDICAL PROTOCOL (HRP-590)

PROTOCOL TITLE: Investigating the causal and phase-dependent role of prefrontal theta oscillations in approach/avoidance behavior

VERSION DATE: 14/09/2024

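### The plan fixes peak versus trough as the primary contrast, but not which behavioural test decides it, and states no multiplicity rule for the behavioural outcome

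*Combined protocol and SAP*

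**What the plan says.** - **Primary outcome.** Section 3.1 names "reaction times to positive and negative emotional stimuli" and ties them to stimulation at theta peaks versus troughs. Section 1.1 frames the purpose around theta phase in the same way. Section 5.2.3 goes further: the reaction times and the "reaction time difference between the congruent and incongruent conditions constitute the primary test outcomes".
- **Behavioural analysis.** Section 15.1 feeds the reaction times into the HDDM and takes from it the "speed of evidence accumulation (drift rate) and the decision thresholds for responding to the stimuli of positive and negative valence". Section 15.3 compares these parameters in a GLMM with "stimulation conditions (real vs control and peaks vs trough) as categorical independent variables". Congruency is not among the listed factors. It then adds that "post-hoc pairwise nonparametric tests will be applied between the conditions".
- **Multiplicity.** The only correction in the plan belongs to the evoked potentials: a "nonparametric cluster-based permutation test with false discovery rate correction for number of comparisons".
- **Sample size.** Section 10.1 states that "a sample size of 26 volunteers will allow us to reach the primary endpoints of this study". Section 15.2 supports this with a single Cohen's d of 0.5, which "will be reached with a sample size of 26 volunteers". It gives no alpha, sidedness, power, contrast or standardising SD.

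**The concern.** The phase contrast is set, but three choices around it are open.

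1. **The measure.** It could be one HDDM parameter, several of them, or the reaction times themselves. The congruency difference that 5.2.3 calls primary has no term in the 15.3 model, so the model as listed cannot test it.
2. **The form of the contrast.** Peak versus trough could be tested within verum blocks only, or as a site-by-phase interaction against vertex stimulation.
3. **The decision rule.** Nothing says whether one positive parameter is enough or all are needed, and nothing adjusts for having several.

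Without these choices, a positive result could be claimed on whichever parameter or pairwise comparison falls below 5%, and the error rate of that claim is above 5%. The secondary outcome has a stated correction and the primary has none. The single d and n in 15.2 cannot be checked against the analysis, because they are not attached to any one test.

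**Working it through.** **Inputs from the protocol:** n = 26 and d = 0.5 (15.2); two stimulation factors (15.3); the measures in 3.1, 5.2.3 and 15.1.

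**Assumptions, none stated in the plan:** alpha 5%; d read as d_z (mean divided by SD of the within-person differences); a paired t test as a proxy for the GLMM; correlation between measures 0 to 0.8.

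**1. Can 26 be reproduced?** Not from the stated inputs alone. With the noncentral t distribution, the noncentrality is d_z × √n = 0.5 × √26 = 2.55 on 25 degrees of freedom.
- One-sided 5% (critical value 1.708): power 79.8%. For 80% power, 27 are needed (25 by normal approximation).
- Two-sided 5% (critical value 2.060): power 68.8%. For 80% power, 34 are needed.

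With d read as d_z, the only match found at a conventional power is one one-sided test. If d is instead in raw-SD units, d_z = 0.5/√(2(1 − r)). Two-sided power at 26 is then 54%, 69%, 89% and 97% for within-person correlation r = 0.3, 0.5, 0.7 and 0.8.

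**2. How many measures?** Two under 3.1 (positive and negative reaction times). Three if the congruency difference is added, or if the parameters are one drift rate and two thresholds. Four if drift rate is also split by valence.

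**3. False-positive chance if any one uncorrected measure counts (two-sided, per contrast).** For independent measures it is 1 − 0.95^k. The values at correlation 0.8 are simulated.

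| Measures | Correlation 0 | Correlation 0.8 |
|---|---|---|
| 2 | 1 − 0.95² = 9.8% | 7.9% |
| 3 | 1 − 0.95³ = 14.3% | 10.1% |
| 4 | 1 − 0.95⁴ = 18.5% | 11.5% |

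With Holm, the rate is 5% or lower throughout.

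**4. Post-hoc pairs.** Two sites by two phases give four cells and 4 × 3/2 = 6 pairs. I simulated four exchangeable conditions with n = 26 and six two-sided signed-rank tests at 5%.
- Run regardless of the model result: about 21% chance of at least one false positive per parameter.
- Run only after a significant 5% omnibus test: about 5% under the complete null.

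Section 15.3 does not state such a gate. A gate also gives no protection when some conditions truly differ and others do not.

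**5. Power of one primary test at realistic numbers.** Section 5.1 recruits up to 26, and 12.1 foresees withdrawals, so 26 is a ceiling. With d_z = 0.5 and two-sided 5%:
- 26 evaluable: 69%
- 24 evaluable (assumed): 65%
- 22 evaluable (assumed): 61%

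At one-sided 5% and 26 evaluable, power is 80%.

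**6. Holm over two measures instead (two-sided, n = 26).** If both measures have d_z = 0.5, the chance that at least one is positive is 1 − (1 − 0.571)² = 82% at correlation 0 and 68% at correlation 0.8. If only one has the effect, Bonferroni power to detect it is 57%.

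**7. If site by phase is chosen.** Suppose d_z = 0.5 is the verum phase effect, vertex stimulation has none, and the SDs are equal. The interaction then has d_z = 0.5/√(2(1 − r)), where r is the correlation of the two phase effects. Two-sided power is 34%, 41%, 52%, 69% and 93% for r = −0.25, 0, 0.25, 0.5 and 0.75. The choice of contrast therefore matters to 15.2.

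**The case against.** The strongest reply is that the plan is more coherent than a quick reading suggests, and much of that reply stands.

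- **A reader might infer that the primary contrast is undefined.** It is not: 1.1 and 3.1 both set theta peak versus trough. What is missing is the measure, and whether phase is tested within verum or against vertex.
- **A reader might infer that the HDDM parameters are a rival primary endpoint.** Section 15.1 presents the HDDM as the analysis of the reaction times, with those times as its input. The gap is narrower: the model returns several parameters and none is named as decisive. The plural in 10.1 also fits the two measures in 3.1, so it is weak evidence of conflict.
- **A reader might take 21% as the plan's post-hoc error rate.** That holds only without a gate. The post-hoc tests follow the GLMM in the text, and a gate may be intended, but it is not written down. Nor does 15.3 say that all six pairs will be tested.
- **A reader might conclude that the study is underpowered.** The documents do not settle this. Power at 26 runs from 54% to 97% two-sided depending on how d was defined, and 15.2 does not say.
- **A reader might treat 16.6 as a further definition of the primary outcome.** It is a privacy answer that loosely groups EEG, questionnaires and task data, and carries little weight here.

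It can also be said that this is a mechanistic study in healthy volunteers with no direct benefit to them (14.1), so a missing decision rule costs less than in an efficacy trial. That is fair and limits the severity. The stated aim is still causal, and nothing else in the documents supplies a behavioural multiplicity rule.

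**Conclusion.** The concern holds as a gap in specification. The deciding behavioural parameter, the form of the phase contrast and the multiplicity rule are not stated, and the congruency difference is called primary without a matching model term. Followed as written, with any uncorrected positive counting, the false-positive chance per contrast is about 8-10% for two measures and 11-19% for four. The post-hoc tests add about 21% per parameter if ungated and about 5% under the complete null if gated. These sizes rest on an assumed two-sided 5% level, correlations from 0 to 0.8 and a paired-test proxy. The gap itself rests on the text alone. It should be corrected, and it matters only if corrected before analysis, since a rule chosen after seeing the results cannot be told apart from selection.

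**What to change.** Before the data are analysed:

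1. **Section 15.3.** Name one HDDM parameter and one peak-versus-trough contrast (within verum, or site by phase) as the single primary test, at a stated alpha and sidedness. Make all other behavioural parameters and all post-hoc pairwise tests secondary and Holm-adjusted.
2. **Sections 3.1 and 5.2.3.** Align them with that test. Either add congruency as a factor in the 15.3 model or stop calling the congruency difference primary.
3. **Sections 15.2 and 10.1.** Restate the power for that one test, with the definition of d and the expected evaluable number. For a within-verum test with d_z = 0.5, the figures in step 5 of the working can be used. For site by phase, say what d refers to and give the assumed correlation.
4. **If Holm over two measures is preferred to a single test,** say so. State that 68-82% for at least one positive assumes d_z = 0.5 on both measures, and that power is 57% by Bonferroni if only one has the effect.

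The cost is protocol text and one analysis rule, with no new data or enrolment. The downside is that some nominally positive results would no longer count, and the stated power may look less favourable.
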